4.18 Data Collection

[figure not shown]
Subjects will have the following data collected:

- *Informed Consent*
- *Subject Demographics*
- *Clinical assessment metrics*
- *Cohort Assignment*
- *Randomization Assignment*
- *Relevant Medical History*
- *Stroke Workflow times (as specified with 'Get with the Guidelines')*
- *NovaGuide System or Lucid M1 System use information*
- *Head inclination (degree)/subject positioning/location of the exam*
- *User (name)*
- *Start/stop time- scan duration*
- *Relevant Concomitant Medications*
- *Device-Related Adverse Events*
- *Device Deficiencies / Technical Observations*

4.19 TCD data collection and data transfer

TCD data will be collected and stored on the NovaGuide System. The details of the data collection and transfer can be found in the User Manual and Data Transfer Instructions.

4.20 Study Workflow

5 MEASURES TO AVOID AND MINIMIZE BIAS

5.1 Imaging Core Laboratory

The objectives of the Core Lab are to provide an unbiased assessment of computed tomography angiography (CTA) to determine presence of large vessel occlusion.

For each subject that received a CTA, the Investigational Site will be instructed to follow a standard procedure developed by the Core Lab for obtaining catheter angiographic images pre-procedure.

Images will be sent directly from the site to the Core Lab. Core Lab definitions and procedures will adhere to specifications documented in the Core Lab Manual of Operations.

5.2 Imaging Core Lab Blinding

The Core Lab will assess all CT/CTA/MRA imaging blinded to cohort assignment. The Investigational Site will ensure subject identifying information is blinded prior to imaging data submission to the Core Lab. Should it not be possible for a site to blind the information without also deleting/omitting information required for evaluation of the angiography or CT/MRI images, NovaSignal shall have the option to contract with the Core Lab to blind the images. Subject's date of birth will be required in order to identify images provided from the study sites.

5.3 TCD Waveform Blinding

There are several methods used to blind both the site clinical team and NovaSignal. First, the clinical team will be blinded to the results of the VCI and therefore will not have the ability to influence specific groups. Additionally, the use of the fully automated system (NovaGuide) will further reduce the influence and variability of an individual clinical researcher. Core Lab will make the assessment of the CTA and NovaSignal will be blinded to the comparison of the VCI and CTA results.

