Great strides have been made in AIS treatment over the last decade; however, lack of a quantitative, bedside/field-based diagnostic severely which is suitable for hospital/prehospital use limits access to treatment. We were able to show positive results in a feasibility study (EXPEDITE) of 66 subjects (33 LVOs) for LVO diagnosis in the ER setting using a newly developed TCD-derived digital biomarker termed Velocity Curvature Index (VCI) [15,16]. The VCI biomarker which leverages a machine learning platform which leverages data produced by the NovaGuide System (NovaGuide Robotic System – K180455, NovaSignal Corp., Los Angeles, CA USA). The NovaGuide, a combination of the Lucid M1 System (510k K160442) and the NovaBot accessory, utilized in both phases of the proposed research plan, is capable of TCD signal acquisition in the hospital setting without need of a trained TCD technician for operation or interpretation. Phase I will establish baseline performance characteristics of the hemodynamic biomarker (VCI) and define the study characteristics and context of use for FDA submission. Phase II will provide a comprehensive, multi-site data set for full analytic validation of the biomarker, with the goal of regulatory submission for an expanded indication. The availability of this biomarker will have several potential applications including, monitoring post-intervention patients and supplement triage and transfer protocols for patients suspected of LVOs, which will result in potentially faster and more widespread access to intervention, affording vastly improved outcomes for thousands of potential patients each year. The analogy to the use of EKG for myocardial infarction (MI) which supplements clinical evaluation and more invasive imaging.

TCD ultrasonography is a safe, non-invasive, and reproducible technique that allows the assessment of cerebral blood flow velocity (CBFV) in the large conducting arteries of the head and neck. TCD data collection relies on the level of experience of a TCD technologist to acquire an accurate and high-quality signal from the intracranial vessel(s) of interest, thus per user, the data quality is variable. NovaSignal has developed the NovaGuide System to assist in the TCD data collection such that consistent high-quality data may be obtained independent of the experience of the user.

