4.6.2 Cohort B Non-LVO

4.6.2.1 *Inclusion Criteria*

A subject must meet all of the following inclusions criteria to be enrolled in the study:

1. * Subject aged 18 years and older
2. (*) Non-large vessel occlusion confirmed by computed tomography angiography (CTA)
3. Subject or Legally Authorized Representative has the ability to provide informed consent and comply with the protocol.

4.6.2.2 *Exclusion Criteria*

A subject cannot be enrolled in the study if any of the following exclusion criteria are met:

1. (*) CTA findings including:
 - a. Occlusions in the common carotid artery, internal carotid artery, anterior carotid artery, middle cerebral artery (M1 and M2 segments), anterior communicating artery, basilar artery, posterior communicating artery and vertebral arteries.
2. (*) Head CT findings consistent with acute primary intracranial hemorrhage (SAH, ICH, etc.)
3. * Hemodynamically unstable patients requiring pharmacological support for hypertension
4. * Subjects who underwent partial or full craniotomy
5. (*) Anticipated insufficient time to acquire a complete set of scans as described by the protocol
6. * Subjects who have a physical limitation preventing placement of the system.

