4.16.2 Lucid M1 System Scanning Technique (Traditional TCD)

If traditional TCD is conducted using the Lucid M1 System alone, measurements will be collected in the MCA at multiple depths ranges between 45 to 65 mm. The MCA scans will be collected from the trans-temporal window by positioning the probe superior to the zygomatic arch. Once cerebral blood flow velocity (CBFV) of the target vessel is found, the TCD operator will hold this position to record 30 seconds of data.

Cohort A TCD will be subjects identified per CTA findings in the Emergency Room (ER), Stroke Care Unit or Imaging Unit as having a large vessel occlusion. A single TCD scan will be collected by a designated TCD operator using the NovaGuide System or the Lucid M1 System alone (manual TCD). The TCD scan will be collected following CTA within a three (3) hour window and prior to standard of care stroke treatment (e.g., mechanical thrombectomy). Note, tPA can be administered prior to TCD measurements. Study measurements will not delay nor interfere with the patients' standard of care treatment. No follow-up scans will be collected.

Cohort B TCD will be subjects identified per CTA findings in the Emergency Room (ER), Stroke Care Unit or Imaging Unit as having a non-large vessel occlusion. A single TCD scan will be collected by a designated TCD operator using the NovaGuide Robotic System or the Lucid M1 System alone (manual TCD). These scans will be collected within a 24-hour period after enrolment and no follow-up scans will be collected.

Cohort C NO TCD will be subjects identified per CTA findings in the Emergency Room (ER), Stroke Care Unit or Imaging Unit as having a large vessel occlusion. No TCD scans will be conducted and subjects followed through to discharge.

Cohort D NO TCD will be subjects identified per CTA findings in the Emergency Room (ER), Stroke Care Unit or Imaging Unit as having a non-large vessel occlusion. No TCD scans will be conducted and subjects followed through to discharge.

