In this work, we will also measure “Get with the Guidelines, Stroke” metrics from each site and compare them to literature, national and site metrics. This will enable us to demonstrate that the system does not adversely affect standard of care for subjects suspected of stroke. The reason we believe it will not affect standard of care is because the device will be used after initial CT and IV-tPA is administered, while the subject is waiting for CTA or intervention. The time window, although short, is available to allow us to measure both the TCD waveform and CTA to confirm VCI is an effective biomarker. Additionally, the times will be compared against the randomized groups (Cohort C and D).

Door to diagnostic imaging. (Statistical demonstration that show we will not delay anything when adding our NovaGuide workflow to), e.g. “Get with the Guidelines, Stroke”: We will calculate the following for subjects that have NovaGuide measurements:

- IV rt-PA arrive by 2 hour, treat by 3 hour: Percent of acute ischemic stroke patients who arrive at the hospital within 120 minutes (2 hours) of time last known well and for whom IV t-PA was initiated at this hospital within 180 minutes (3 hours) of time last known well.
- % Door to CT \leq 25 minutes: Percent of patients who receive brain imaging within 25 minutes of arrival.
- Door to Puncture (DTP) Time within 90 minutes: (Percentage of patients with acute ischemic stroke who receive mechanical endovascular reperfusion)

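### Section 5.3 infers from blinding to VCI that no cohort can be influenced, but nothing masks the TCD operator to CTA or cohort when the signal is acquired

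*Combined protocol and SAP*

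**What the plan says.** On blinding, Section 5.3 says "the clinical team will be blinded to the results of the VCI and therefore will not have the ability to influence specific groups". It adds that the automated NovaGuide reduces the influence of individual researchers further, and that the Core Lab assesses the CTA.

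On the order of events, Section 4.16.2 says "Cohort A TCD will be subjects identified per CTA findings in the Emergency Room (ER), Stroke Care Unit or Imaging Unit" as having an LVO. For that cohort, "The TCD scan will be collected following CTA within a three (3) hour window and prior to standard of care stroke treatment". Cohort B is also defined by CTA at entry (Section 4.6.2: "Non-large vessel occlusion confirmed by computed tomography angiography (CTA"), but its scan window is different: "These scans will be collected within a 24-hour period after enrolment and no follow-up scans will be collected".

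On the device, Section 4.16.2 says "A single TCD scan will be collected by a designated TCD operator using the NovaGuide System or the Lucid M1 System alone (manual TCD". Section 2 says that TCD acquisition depends on the technologist's experience, "thus per user, the data quality is variable".

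On timing, Section 11.1 describes the device as being used "while the subject is waiting for CTA or intervention".

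**The concern.** The VCI result is the output of the index test. Hiding it stops the team from acting on the answer. It does not hide the reference standard from the person who acquires the waveform. If that person is aware of the local CTA result, search effort, the signal accepted and the time of stopping can differ between LVO and non-LVO subjects for reasons other than blood flow.

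AUC, sensitivity and specificity of VCI against CTA are the primary endpoint in both phases (Sections 4.2.1 and 4.2.2), with AUC targets of 85% and 90% (Sections 11.1 and 11.2). Section 2 gives regulatory submission as the goal of the Phase 2 data. Blinded processing after the scan cannot restore a signal that was acquired differently. A reader of Section 5.3 would take it that the design excludes this.

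**Working it through.** The point rests on the text, so the sections are set side by side first. The arithmetic after that is illustrative.

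**1. Order of events.** CTA findings are entry criteria for both cohorts (Sections 4.6.1 and 4.6.2). Randomization to TCD or no TCD follows eligibility and consent, within cohort, and the site enters the occlusion location at that step (Section 4.9). Scanning comes after: within 3 hours of CTA in Cohort A, and within 24 hours of enrolment in Cohort B (Sections 4.15 and 4.16.2). The unequal windows can themselves reveal the cohort.

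**2. Who is masked to what.**

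| Role | Stated masking | Section |
|---|---|---|
| Clinical team | VCI result | 5.3 |
| Core Lab reading CTA | Cohort assignment | 5.2 |
| Sponsor assessing TCD data | Study and radiology report data | Synopsis (TCD Data Analysis), 11.4 |
| TCD operator | Nothing on CTA or cohort | none found |

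The Synopsis applies the sponsor's blinded assessment to NovaGuide and Lucid M1 data. Section 11.4 names NovaGuide data only.

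**3. What the operator can still vary.** No rule says which device is used. With the manual probe, the operator decides how hard to search and at which depths within 45 to 65 mm (Section 4.16.2). With NovaGuide, the system searches by itself, but the team may end the session at any time within the 20-minute monitoring period (Section 4.16.1). The automation safeguard in Section 5.3 covers NovaGuide scans only. Section 4.11 provides for a quality review of de-identified data, but gives no criteria and names no reviewer.

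**4. Timing conflict.** The part of Section 11.1 about waiting for CTA cannot be squared with CTA-based entry and randomization (Sections 4.6 and 4.9) or with scanning after CTA in Cohort A (Section 4.16.2). The part about waiting for intervention can.

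**5. Scale, for illustration.** The documents give no figure for an acquisition effect. The plan's Phase 2 precision serves as a yardstick. The Hanley-McNeil formula is SE² = [A(1−A) + (m−1)(P−A²) + (n−1)(R−A²)]/(mn), with P = A/(2−A) and R = 2A²/(1+A). For A = 0.90 and m = n = 150:

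- P = 0.8182, R = 0.8526, A² = 0.81
- SE² = [0.09 + 149 × 0.0082 + 149 × 0.0426]/22,500, so SE = 0.0185
- 1.645 × 0.0185 = 0.030, lower bound 0.870

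This reproduces the 3% and 87% in Section 11.2.

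Now assume equal-variance binormal VCI distributions, so that AUC = Φ(d/√2). For AUC 0.85, d = √2 × Φ⁻¹(0.85) = 1.466. Let acquisition change the separation by s SD:

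| s (assumed) | (1.466 + s)/√2 | AUC |
|---|---|---|
| −0.35 | 0.789 | 0.785 |
| −0.20 | 0.895 | 0.815 |
| 0 | 1.037 | 0.850 |
| +0.20 | 1.178 | 0.881 |
| +0.35 | 1.284 | 0.900 |

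Both signs are shown because the documents do not settle the direction. Against the Phase 2 yardstick, d is 1.593 at AUC 0.87 and 1.812 at 0.90. A shift of 1.812 − 1.593 = 0.22 SD would therefore span the whole 3-point margin.

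**The case against.** The case on the other side is substantial, and much of it stands.

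- **Later steps are blinded.** A reader might infer that the index test as a whole is unblinded to the reference standard. The documents do not support that: VCI assessment and Core Lab reading are both stated to be blinded. Only acquisition is unmasked, and only to the local CTA result.
- **Operator knowledge is not stated.** A reader might also infer that the operator knows the cohort. No section says so. In Section 4.9 it is the site that enters occlusion location, the workflow figure in Section 4.20 is not shown, and detailed scanning steps are left to a User Manual. What can be said is that the workflow makes the information available and that no provision withholds it.
- **Discretion is bounded.** Manual recordings are fixed at 30 seconds and depth at 45 to 65 mm, NovaGuide positions its own probes, and beats are averaged (Section 3.5). The quality review in Section 4.11 means that the operator need not be the only judge of signal quality. So recording length is not a free choice in manual scans. Device choice, manual search effort and depth within range, and early ending of a NovaGuide session remain.
- **Inflation is not shown.** The operator does not see VCI, and nothing in the documents shows that a longer search or another depth moves VCI toward the known cohort. Added noise could lower the AUC.
- **The timing conflict is a separate matter.** A scan made before CTA would be acquired without knowledge of it, so the wording in Section 11.1 does not support the masking point.

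None of this rescues the inference in Section 5.3. Its own remark that automation reduces individual influence further implies that some influence remains.

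**Conclusion.** The sentence in Section 5.3 is wrong as written. Masking the VCI result does not mask the operator to CTA or cohort, and no other section does so. Acquisition of the index test is not masked to the local CTA result, and most discretion remains where the manual device is used.

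The size and direction of any resulting bias are unknown. The AUC movements above rest on an assumed binormal equal-variance model and on assumed shifts in every scan; they show sensitivity and are not estimates. They do not support a conclusion that the trial's AUC will be inflated. The study can proceed, but the statement should be corrected and acquisition made auditable before the Phase 2 data are used for validation.

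**What to change.** 1. In Section 5.3, replace the sentence with a statement that the operator is not masked to CTA or cohort at acquisition, and that only VCI computation and Core Lab CTA reading are blinded.
2. Require upload of every recorded depth and side. Turn the quality review in Section 4.11 into a prespecified automated rule, run blind to cohort, that selects the analysed segment and accepts or rejects the scan. Report rejected scans by cohort.
3. Report AUC, sensitivity and specificity separately for NovaGuide and manual scans, and the device mix by cohort. Section 4.18 already collects the device information.
4. State in Section 11.4 that the blinded assessment covers Lucid M1 data, as the Synopsis does.
5. Separately, reconcile the wording on waiting for CTA in Section 11.1 with Sections 4.9 and 4.16.2.

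Device should not be fixed by site: that would confound device with the site comparison planned in Section 11.2.

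These changes do not mask the operator, and differences in search effort could persist. They disclose the limitation, take selection of the analysed segment and scan acceptance out of unblinded hands, and let a reader see whether results depend on the device. The cost is protocol wording, a coded rule, slightly more analysis and a less favourable blinding statement.

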6 RISKS AND BENEFITS

There is minimal potential clinical risk associated with the scans described in the study. The risks associated with the use of the NovaGuide System in humans have not been determined as this study is one of the initial uses of the device. *An ongoing study utilizing the device in subjects experiencing neurological symptoms of stroke has not reported any unexpected or serious device related adverse events (Protocol No.: NA-01STR-01).* The NovaGuide System is designed to be physically and electro-mechanically safe according to manufacturing standards. At any time, for any reason, the use of the device can be discontinued. Additionally, the FDA cleared version of the NovaGuide System is in commercial deployment in the US and Europe and no unexpected or serious device related events have been reported.

There is no direct benefit to the subject participating in the study.

7 DEVICE-RELATED ADVERSE EVENTS

Collection of device-related adverse events will start after the time that informed consent form is obtained. Device-related adverse events will be monitored throughout the study.

All suspected device related adverse events shall be recorded on the Adverse Event page of the CRF, if they are suspected to be related to the use of the NovaGuide System. If appropriate, the event shall subsequently be reported to the relevant IRB. The event shall be thoroughly investigated and a causal relation as to whether the event is related or not to the use of the NovaGuide System shall be established.

Events which are required to be reported and/or considered to be serious are categorized into either Serious Adverse Events (SAE), Unanticipated Serious Adverse Device Effect (UADE/USADE) or all Serious Adverse Device Effects (SADE) and include the following:

Adverse event that:

- a) Led to a death
- b) Led to a serious deterioration in the health of the subject that:
 - 1) resulted in a life-threatening illness or injury
 - 2) resulted in a permanent impairment of a body structure or a body function
 - 3) required in-patient or prolongation hospitalisation
 - 4) resulted in medical or surgical intervention to prevent life-threatening illness or injury or permanent impairment to body structure or a body function
- c) Led to foetal distress, foetal death or a congenital abnormality or birth defect.

NOTE: Planned hospitalization for a pre-existing condition, without serious deterioration in health, is not considered a serious adverse event.

Device deficiencies are also reportable if they did not lead to an adverse event but could have led to a SADE:

- a) if either suitable action had not been taken,
- b) if intervention had not been made, or
- c) if circumstances had been less fortunate

NOTE: Device deficiencies include inadequacies of a medical device with respect to its identity, quality, durability, reliability, safety or performance.

The Investigator will record the nature, severity, relatedness, treatment and outcome of the AE. This classification of the event determines the reporting procedures to be followed. NovaSignal may upgrade the classification as required for reporting purposes.

At the initiation of device use through end of use of the device, all subjects with adequate quality NovaGuide System data shall be assessed for any potentially device related complications or adverse events. All events shall be followed until resolution or through the end of a subject's study participation.

7.1 Potential or Anticipated Device Related Adverse Events/Complications

The following device related adverse events have been identified as possible (anticipated) with the use of the NovaGuide System:

- Physical discomfort of the head and neck due to pressure from the probe, or probe accidentally coming in contact with ears, eyes or hair.
- Psychological feeling of claustrophobia- the fear of being enclosed in a small space.

7.2 Unanticipated Adverse Device Effect (UADE)

An Unanticipated ADE (UADE) is any serious adverse effect on health or safety or any life-threatening problem or death caused by or associated with a device, if that effect, problem, or death was not previously identified in nature, severity, or degree of incidence in the application; or any other unanticipated serious problem associated with a device that relates to the rights, safety, or welfare of subjects.

7.3 Reporting Adverse Events

Device-related adverse events information will be collected throughout the study. From the initiation of and end of device use, all subjects scanned with the NovaGuide System shall be assessed for any potentially device related complications or adverse events. All events shall be followed until resolution or through the end of a subject's study participation.

Event, onset date, severity, relatedness, device relationship, treatment and outcome of the AE will be recorded on the appropriate case report form. Any device-related AEs will be monitored until they are adequately resolved or explained. This classification of the event determines the reporting procedures to be followed. For purposes of this protocol, the following definitions will apply.

